4.3.2.2. Analysis Related to the Efficacy Estimand

The analysis related to the efficacy estimand will be conducted utilizing data in the EAS.

For the mean percent body weight change from randomization, a MMRM will be conducted. Restricted maximum likelihood (REML) will be used to obtain model parameter estimates and

the Kenward-Roger option will be used to estimate the denominator degrees of freedom. The response variable of MMRM will be the percent change in body weight from baseline values obtained at each scheduled postbaseline visit.

For the MMRM model, the independent variables of analysis model are treatment group, visit, treatment-by-visit interaction, and stratification factors (country/pooled country, sex, and tirzepatide MTD dose at randomization) as fixed effects, and body weight at randomization (Week 36) as a covariate. An unstructured covariance structure will model relationship of within-patient errors. If this model fails to converge, the following variance covariance structures will be tested in order until convergence is achieved:

- heterogeneous Toeplitz
- heterogeneous first order autoregressive
- heterogeneous compound symmetry
- Toeplitz
- first order autoregressive, and
- compound symmetry.

The first covariance structure that converges will be used.

With the aid of the MMRM analysis, 2-sided 95% CIs for mean percent change in body weight from randomization to the 88-week visit for tirzepatide MTD compared to placebo will be derived and summarized. The resulting LSM estimates of mean percent change in body weight from baseline will be plotted by visit and by study treatment.

4.3.2.3. Hybrid Methods of Imputation

For efficacy analyses relative to the treatment regimen estimand, the intercurrent events and the resulting missing values will be handled as follows:

- **Category 1:** for missing data solely due to an exceptional circumstance, such as a pandemic or natural disaster (after other reasons for missing data are ruled out), considers the missing data as missing at random. The missing data will be imputed using all nonmissing data of the primary outcome measurement from the same treatment arm.
- **Category 2:** for missing data due to all other intercurrent events, it will be imputed based on retrieved dropouts in the same treatment arm, defined as observed primary outcome measurements, from participants in the same treatment group who had their efficacy assessed after early discontinuation of study drug. In cases where there are not enough retrieved dropouts to provide a reliable imputation model (for example, the model implemented by the SAS program does not converge), an alternative multiple imputation method with reference to the placebo group (ie, placebo multiple imputation) will be used.

In cases where placebo multiple imputation method is used for missing data imputation in Category 2 because of not enough retrieved dropouts, the missing data in Category 1 will be imputed using all nonmissing data of the primary outcome measurement from the placebo group.

4.3.2.4. Sensitivity Analysis

For submission of Study GPHN to the US FDA tirzepatide application for chronic weight management, additional sensitivity analyses of the primary efficacy outcomes will be conducted using the FAS and guided by the “treatment-regimen” estimand, which represents the efficacy irrespective of adherence to study drug. This assessment will analyze percent change in body weight obtained at the 88-week visit using an ANCOVA model. The terms of the model will be the same as specified in Section 4.3.2.1. These analyses are intended to assess the robustness of primary efficacy results using different missing data imputation methods:

- Retrieved dropout multiple imputation: Missing values of change in body weight at the 88-week visit will be imputed based on observed body weight change from randomization (Week 36) values at the visit from participants in the same treatment group who had their efficacy assessed after early discontinuation of study drug. In cases where there are not enough retrieved dropouts to provide a reliable imputation model (for example, the model implemented by the SAS program does not converge), the placebo multiple imputation method (described below) will be used.
- Placebo multiple imputation: Missing values of change in body weight at the 88-week visit will be imputed based on observed body weight change from randomization (Week 36) at the visit from participants in the placebo treatment group.
- 2-way tipping point analysis: The analysis will begin with the primary analysis aligned to treatment regimen estimand and adding positive and negative penalties simultaneously to both the tirzepatide MTD arm and the placebo arm, considering when results tip from superiority to inconclusive, and then considering the clinical plausibility of such scenarios.

4.4. Secondary Endpoint(s) Analysis

4.4.1. Main Analytical Approach for Categorical Outcome Related to Weight Measurement

For both treatment regimen and efficacy estimand, a logistic regression model will be used. For the proportion of patients achieving weight loss target since

- Baseline (Week 0), the following covariates will be included: treatment group, country/pooled country, sex, and tirzepatide MTD dose at randomization, and body weight at randomization (Week 36) and at baseline (Week 0).
- Randomization (Week 36), the following covariates will be included: treatment group, country/pooled country, sex, and tirzepatide MTD dose at randomization (Week 36), and body weight at randomization (Week 36).

For missing data imputation:

- For treatment regimen estimand: missing data will be handled by hybrid imputation of missing body weight at Week 88 (see Section 4.1 and Section 4.3.2.3 for details).

- For efficacy estimand: missing data will be handled by predicted value from MMRM analysis followed by dichotomization. When MMRM is used, variance-covariance structure for within-patient errors will be same as Section 4.3.2.2.

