1.2.2. Estimands for Secondary Endpoints

Table GPHN.1.2. Attribute Description of Secondary Estimands

Secondary Estimand	Population	Endpoint	Treatment condition of interest	Handling of intercurrent events	Population-level summary
Key secondary related to mean change	Same as primary estimand	As described in Table GPHN.1.1	For primary disclosure of Study GPHN including submission to the US FDA, follow the same manner of the treatment regimen estimand in Section 1.2.1; for all other purposes, the same manner of the efficacy estimand in Section 1.2.1	For primary disclosure of Study GPHN including submission to the US FDA, follow the same manner of the treatment regimen estimand in Section 1.2.1; for all other purposes, follow the same manner of the efficacy estimand in Section 1.2.1	Difference in mean changes between treatment conditions
Key secondary related to percentage of participants meeting certain criteria					Difference in percentage of participants between treatment conditions as assessed by odds ratio
Key secondary related to time to meet certain criteria					Difference in time to response between treatment conditions
Additional secondary related to mean change	Same as primary estimand	As described in Table GPHN.1.1	Follow the same manner of the efficacy estimand in Section 1.2.1	Follow the same manner of the efficacy estimand in Section 1.2.1	Difference in mean changes between treatment conditions
Additional secondary related to percentage of participants meeting certain criteria					Difference in percentage of participants between treatment conditions as assessed by odds ratio

Abbreviation: FDA = Food and Drug Administration.

[figure not shown]
Unless otherwise specified, the attributes of estimands supporting exploratory objectives will follow the same manner of the efficacy estimand in Section 1.2.1, with the exception of endpoints and population-level summary, which will be objective specific.

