2.1. Multiplicity Adjustment

The type 1 error rate control strategy for primary and key secondary efficacy objectives is documented in [Figure GPHN.2.1](#). Both efficacy estimand and treatment regimen estimand will be used to assess those objectives. As they are intended for different purposes, no multiplicity adjustments will be made for conducting separate analyses relative to the efficacy and treatment regimen estimands. In addition, no multiplicity adjustments will be made for evaluating additional secondary and exploratory objectives and safety assessments.

[figure not shown]

Figure GPHN.2.1. GPHN type 1 error control strategy for primary and key secondary efficacy endpoints.

3. Analysis Sets

For purposes of analyses, [Table GPHN.3.1](#) defines the analysis population and analysis sets.

Table GPHN.3.1. Description of Analysis Population and Analysis Datasets

Population/Analysis Set	Description
Entered	All participants who sign informed consent.
Enrolled	All participants who are assigned to open-label tirzepatide treatment.
Randomized	All participants who are randomly assigned a study treatment (double-blind).
Modified Intent-to-Treat (mITT)	All enrolled participants who are exposed to at least 1 dose of study drug.
Efficacy Analysis Set (EAS)	Data obtained during double-blind treatment period from mITT, excluding data after discontinuation of study drug (last dose date + 7 days).
Full Analysis Set (FAS)	Data obtained during double-blind treatment period from mITT, regardless of adherence to study drug.
Safety Analysis Set (SS)	Data obtained during double-blind treatment period and safety follow-up period from mITT, regardless of adherence to study drug.

Unless otherwise specified, for analyses guided by the treatment regimen estimand, FAS will be used. For analyses guided by the efficacy estimand, EAS will be used, and for safety analysis, SS will be used.

For open-label period analysis, the analysis set is defined in Section [6.4.1](#).

For immunogenicity analysis, the analysis set is defined in Section [4.6.5.5](#).

4. Statistical Analyses

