Unless specified otherwise, for analyses in the double-blind treatment period, baseline is defined as the last nonmissing data collected prior to or at randomization (Week 36); for analyses including data collected in open-label lead-in period, baseline is defined as the last nonmissing data collected prior to or at study enrollment (Week 0).

For some specific safety related parameters, the definition of baseline and postbaseline for double-blind treatment period are specified in [Table GPHN.4.1](#).

The definition of baseline and postbaseline during the open-label lead-in treatment period can be found in [Appendix 4](#).

Table GPHN.4.1. Baseline and Postbaseline Definitions for Safety Outcomes in Double-Blind treatment Period

Analysis Set	Analysis Type	Baseline	Postbaseline
SS	1.1) Treatment-Emergent Adverse Events	Ongoing at the time of the randomization to the double-blind treatment period.	Starts after randomization visit and ends after the whole study period (including off-drug follow-up visit).
SS	1.2) Treatment-Emergent Abnormal Labs ^a , Vital Signs, and ECGs.	Refer to Table GPHN.6.1 for baseline definition.	Postbaseline will be defined as above (1.1). All scheduled and unscheduled measurements will be included.
SS	1.4) Change from Last Baseline to Week xx and to Last Postbaseline for Labs ^a , Vital Signs, and ECGs.	The last scheduled and unscheduled non-missing assessment recorded during the open-label lead-in period.	Postbaseline will be defined as above (1.1). Only scheduled visits will be included. The ED visits are considered scheduled visits.

Abbreviations: ECGs = electrocardiogram; ED = early discontinuation; SS = Safety Analysis Set.

^a Immunogenicity-related analysis is specified in Section [4.6.5.5](#).

For the primary and key secondary efficacy endpoint analyses subject to type 1 error rate control, data for participants with missing values at the 88-week visit (or weight-related measurements at 64-week visit) will be imputed based on the method described in Section [4.3.2.3](#). Otherwise, missing values will not be explicitly imputed except for the parameters with only 1 postbaseline measure during the analysis period per schedule of activity, where LOCF approach will be applied to impute the endpoint when ED measure is available.

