4.3.2. Main Analytical Approach

4.3.2.1. Analysis Related to the Treatment Regimen Estimand

The analysis related to the treatment regimen estimand will be conducted using the FAS.

The analysis for the mean percent change in body weight will be conducted utilizing ANCOVA. The response variable for the ANCOVA model will be percent change in body weight from randomization to Week 88. This model will include terms of treatment group, country/pooled country, sex, tirzepatide MTD dose at randomization, and body weight at randomization (Week 36) as covariates. The ANCOVA analysis will be conducted with multiple imputation of missing data guided by hybrid method at Week 88 (see Section 4.1 and Section 4.3.2.3 for details) and statistical inference over multiple imputation of missing data guided by Rubin (1987).

With the aid of the ANCOVA model, 2-sided 95% CI for mean percent change in body weight from baseline to the 88-week visit between tirzepatide MTD and placebo will be derived.

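### Efficacy estimand: responder endpoints H4, H6, H7, H9 and H10 dichotomise one MMRM prediction for each missing Week 88 weight, which usually distorts the odds ratio and leaves imputation uncertainty out of its standard error

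*SAP*

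**What the plan says.** SAP 4.4.1 gives a separate missing-data rule for each estimand. The treatment regimen estimand gets the hybrid imputation of SAP 4.3.2.3. For the efficacy estimand, "missing data will be handled by predicted value from MMRM analysis followed by dichotomization". Nothing in that bullet mentions a residual or parameter draw, a number of imputations or pooling.

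Elsewhere the SAP is explicit. The treatment regimen ANCOVA in 4.3.2.1 "will be conducted with multiple imputation of missing data guided by hybrid method at Week 88", with inference by Rubin's method. The sensitivity analyses in 4.3.2.4 also use multiple imputation, but only for the primary outcome under the treatment regimen estimand.

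Table GPHN.4.2 sends H4 (maintaining at least 80% of the lead-in loss) and H6, H7, H9 and H10 (losses of 5, 10, 15 and 20% from Week 0) to 4.4.1. Their population-level summary in Table GPHN.1.2 is: "Difference in percentage of participants between treatment conditions as assessed by odds ratio". On the objectives under type 1 error control, SAP 2.1 says: "Both efficacy estimand and treatment regimen estimand will be used to assess those objectives". The Efficacy Analysis Set in Table GPHN.3.1 is defined as "excluding data after discontinuation of study drug (last dose date + 7 days".

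SAP 4.1 contains a broader sentence that begins "For the primary and key secondary efficacy endpoint analyses subject to type 1 error rate control, data for participants with missing values" and points to 4.3.2.3 without naming an estimand. Section 4.3.2.3 opens: "For efficacy analyses relative to the treatment regimen estimand, the intercurrent events and the resulting missing values will be handled as follows".

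**The concern.** A predicted value is a mean without residual scatter. Someone predicted just past the cut-off has close to an even chance of being a responder, yet is coded as a certain yes or no. Two consequences follow.

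- Filled-in weights vary less than real weights, so responder rates among the filled-in participants move to the majority side of the threshold in each arm. With a true effect and similar dropout, this usually pushes the odds ratio away from 1.
- The logistic standard error treats the filled-in outcomes as observed and carries no imputation uncertainty.

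Everyone who stops drug early enough to have no usable Week 88 weight in the Efficacy Analysis Set is handled this way. At stake are the efficacy-estimand odds ratios, intervals and per-test error rates for five type-1-controlled endpoints, and the exploratory responder endpoints in Table GPHN.4.4 that refer to 4.4.1. SAP 4.1 also appears to prescribe a different method for the same analyses.

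**Working it through.** **1. The plan's own figure.** SAP Section 5 gives 300 per arm, difference 6, SD 8, 25% dropout and two-sided alpha 0.05. That leaves 300 × 0.75 = 225 per arm, with noncentrality 6 / (8 × √(2/225)) = 7.96 and power above 99.99%. The stated power of more than 90% is met. It concerns the primary endpoint only; the SAP gives no figure for the responder endpoints.

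**2. One participant.** Assume a correlation of 0.73 between Week 64 and Week 88 (random-walk pattern). For someone last weighed on treatment at Week 64, predictions have SD 8 × 0.73 = 5.8 instead of 8, and the residual SD is 8 × √(1 − 0.73²) = 5.5. If the prediction is 2 points on the responder side, the chance of response is Φ(2/5.5) = 0.64. The rule codes it as 1.

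**3. Why H4 is exposed.** With lead-in loss L, maintaining 80% of it means a change from Week 36 of at most 0.2L/(1 − L). At an assumed L = 18% this is 0.036/0.82 = +4.4%, which lies between assumed arm means of +6 (placebo) and 0 (tirzepatide). Filled-in placebo outcomes drift to non-response and tirzepatide outcomes to response. The H6 cut-off is 0.95/0.82 − 1 = +15.9%, above both means, so both arms drift to response. If placebo loses more participants, its rate rises more and the bias can reverse.

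**4. Simulation inputs.**
- From the plan: 300 per arm, SD 8, 6-point difference, 25% dropout, and the 4.4.1 logistic covariates. H4 was run with both covariate lists, because the SAP does not say which applies.
- Assumed, population: 70% women; Week 0 weight mean 115 kg (men) or 102 kg (women), SD 20; four country groups; 85% on 15 mg.
- Assumed, weights: mean lead-in loss 12, 15, 18 or 20%, independent of later change; Week 88 change +6/0, +3/−3 or +10/+4 (placebo/tirzepatide); weights at Weeks 40, 52, 64, 76 and 88; two visit-correlation patterns.
- Assumed, dropout: completely at random, with the last on-treatment weight at Week 36, 40, 52, 64 or 76 with equal probability.
- Prediction: on the covariates and the participant's own earlier weights.

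Equal dropout gives 4 × 3 × 2 = 24 settings with an effect; each unequal split has 12. There were at least 1000 runs per setting. Bias is relative to complete data.

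| | OR bias, equal 25% | 95% CI coverage, equal 25% | OR bias, 35% placebo / 15% tirzepatide | OR bias, 15% placebo / 35% tirzepatide | Rejection, no true difference, equal 25% |
|---|---|---|---|---|---|
| H4 | +6 to +39% | 50-91% | −1 to +39% | +2 to +40% | 7-15% |
| H6 | +5 to +22% | 80-95% | −10 to +21% | +23 to +30% | 6-9% |
| H7 | +9 to +24% | 79-94% | 0 to +25% | +11 to +28% | 7-10% |
| H9 | +9 to +21% | 82-93% | +13 to +27% | −2 to +26% | 6-9% |
| H10 | +3 to +20% | 83-97% | +20 to +30% | −10 to +19% | 5-9% |

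With complete data, null rejection was 4-6%. With no true difference and equal dropout the odds ratio stayed at 0.98-1.02. With no true difference and 35/15 dropout it was 0.83-1.16, with rejection of 13-16% for H4 and 7-10% for the others.

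**5. Worked example** (L = 18%, +6/0, random walk, equal dropout). H4 responder rates of 43% vs 71% became 41% vs 74%. The raw odds ratio goes from (0.71/0.29)/(0.43/0.57) = 3.25 to (0.74/0.26)/(0.41/0.59) = 4.10. The adjusted odds ratio went from 3.42 to 4.62, and 4.62/3.42 = 1.35. Coverage was 60%. Separately programmed repeats gave 3.36-3.44 becoming 4.55-4.63, coverage 55-61%.

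**6. Standard error.** With no true difference (both arms +3), the H4 model SE was 0.173 against an actual SD of 0.223, a ratio of 0.776. The nominal 5% test then rejects with probability 2 × [1 − Φ(1.96 × 0.776)] = 2 × [1 − Φ(1.52)] = 12.9%. The simulated rate was 13.0%.

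**7. Different assumptions.** A second simulation used 400 runs per scenario and lead-in loss of 20 or 12%. Dropout was completely at random, dependent on observed weights, or 35% placebo / 15% tirzepatide. It gave H4 +18 to +31% with coverage 69-83%. The other endpoints ranged from −4 to +20% with coverage 86-95%. Null rejection was 3-9%.

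**The case against.** The strongest reply is that 4.4.1 is silent on draws and does not forbid them, and that little depends on the answer. Primary disclosure and the FDA submission use the treatment regimen estimand. At the planned effect, rejection stayed within 3 points of complete data when dropout was equal. That limited reach is real and keeps the point below the most serious grade. Silence is not a defence: the SAP says multiple imputation where it means it, and either reading needs the same sentence added.

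The size is also open to challenge. The example lies towards the upper end of the range. One in five simulated dropouts has no weight after randomisation; when every dropout had at least one, H4 bias fell to +24% with coverage 76%. The plan's 25% is a dropout rate for power and need not equal the share without an on-treatment Week 88 weight. At 10% dropout the example gives +12% for H4 (coverage 88%) and +5 to +8% for the others. High null rejection for H4 needs arm means near its cut-off. These points stand, and only ranges should be quoted.

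A reading in which the prediction ignores the participant's own weights would be far worse (H4 +86 to +97% in the example). It is less likely, because 4.4.1 also specifies a within-patient covariance structure.

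Finally, the sentence in 4.1 can be seen as a loose cross-reference that the more specific 4.4.1 overrides. That is probably how it would be applied, but the text should say so.

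**Conclusion.** The concern holds for the efficacy estimand. Following 4.4.1 as written leaves imputation uncertainty out of the standard errors for H4, H6, H7, H9 and H10, and it usually overstates the odds ratio when there is a true effect. At equal 25% dropout the overstatement was 3-39% across the settings. H4 had the largest bias in 18 of 24, but that ordering reflects the assumptions and is not a general ranking of the endpoints.

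Direction and size depend on lead-in loss, arm means, visit correlations and dropout by arm and timing. The documents give none of these beyond a single dropout rate. With unequal dropout the bias can vanish or reverse, and power for H6 or H10 fell by up to 10 points.

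Treatment regimen results and the continuous MMRM analyses are not affected. The familywise error rate cannot be judged, because Figure GPHN.2.1 is not shown.

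**What to change.** In SAP 4.4.1, replace the efficacy-estimand bullet with multiple imputation under missing at random, for example 100 imputations, drawing both parameters and residuals.

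- **Imputation model:** the 4.3.2.2 terms, namely treatment, visit and their interaction, plus these: "stratification factors (country/pooled country, sex, and tirzepatide MTD dose at randomization) as fixed effects, and body weight at randomization (Week 36) as a covariate", with on-treatment weights as responses, unstructured covariance, and Week 0 weight added. Week 0 weight is in the 4.4.1 logistic model for losses from Week 0 but not in 4.3.2.2. Leaving it out shrank the imputed odds ratios by about 4% when lead-in loss was allowed to correlate with later change. The percent-weight-loss stratum is in neither model and is not needed.
- **Analysis:** dichotomise each completed dataset, fit the same logistic model and pool the log odds ratios by Rubin's rules, as 4.3.2.1 already does.
- **SAP 4.1:** limit the sentence that points to 4.3.2.3 to the treatment regimen estimand.
- **If the predicted-value rule is kept as a supplementary analysis:** state whether it uses the participant's own earlier weights.

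The cost is SAP wording and a few lines of programming; design and sample size do not change. In the example, multiple imputation gave odds ratios of 4.04, 3.73, 3.65, 3.62 and 3.46 (H6, H7, H9, H10, H4) against 4.02, 3.73, 3.65, 3.66 and 3.44 with complete data. Intervals become slightly wider and mildly conservative: simulated coverage was 95-99% and null rejection 2-3%. In the unequal-dropout case run, H6 rejection was 91%, against 93% with complete data and 85% with the predicted-value rule.
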